4.10. Sample size considerations

As of 20 April 2020, there are 96,224 individuals tested for SARS-CoV-2 and 7,515 are tested positive. A total of 364 patients with a positive test have died (4.8%). The proportion of patients using ACE-I/ARB is expected to be 17% and the proportion using CCB is expected to be 7% based on data from a historical cohort of patients with influenza or pneumonia ([name] et al., article submitted).

Assuming a 30-day mortality of 4% in unexposed, we will have a power of 92% for detecting a RR of 1.2 with an alpha-level of 5% in the comparison of current ACE-I/ARB users with non-users. (EpiSheet).

5. Ethical/data protection issues

According to Danish law, registry-based studies do not require informed consent or ethical committee approval. Only aggregated data will be published.

All data are pseudonymized and stored at secured serves at the Danish Health Data Authority. Data management and analyses are performed through secure remote access to these servers. Data management and analyses will be conducted and checked by experienced researchers.

6. Plans for communication of study results

[figure not shown]
The study protocol will be registered in the EU PAS registry. Results will be communicated through international peer-reviewed journals and the website of the Danish Medicines Agency. Any evidence of adverse effects of ACE-I/ARB will be communicated to the Danish Medicines Agency.

7. Amendments and deviations

Any future amendments or deviations from the study protocol will be included in this section.

Figure. Study design diagram

Study design

Codes

	Source/	Look-	Inclusion codes	Exclusion
	coding	back		codes
Exposures (ATC codes)				
Number of antihypertensives	NPD/ATC	90d	0-5 (see below: ACE-I/ARB, CCB, Thiazides/diuretics, BB, other antihypertensives)	
ACE-I	NPD/ATC	90d	C09A, C09B	
ARB	NPD/ATC	90d	C09C, C09D	
Calcium channel blockers (CCB)	NPD/ATC	90d	C07FB, C08CA, C09BB, C09DB, C09DX01	
Thiazides/diuretics	NPD/ATC	90d	C03AA01, C03AA03, C03AB01, C03AB03, C03AX01, C03EA, C07B, C09BA, C09DA, C09DX01, C09DX03, C09XA52, C09XA54	C07BA06 C09BA04
Beta-blockers (BB)	NPD/ATC	90d	C07	
Other antihypertensives	NPD/ATC	90d	C02AC, C02CA, C03BA11, C09XA C02AB01	C09XA54
Outcomes				
ICU admission (procedure code)	DNPR/Procedure		NABE, NABB	
Mechanical ventilation (procedure code)	DNPR/Procedure		BGDA0	
Acute renal replacement therapy (RRT) (in patients without chronic RRT)	DNPR/Procedure		BJFD0	BJFD2 (any codes within prior 12 months)
Treatment with inotropes/vasopressors	DNPR/Procedure		BFHC92A, BFHC92B, BFHC92C, BFHC92D, BFHC92E, BFHC93A, BFHC93B, BFHC93C, BFHC95	
Covariates				
Age	CPR			
Sex	CPR			
Calendar time (before / after lockdown)	DNPR			
Hospital-diagnosed hypertension	DNPR/ICD-10	10y	110, 115	
Stable angina pectoris (without procedures)	DNPR/ICD-10	10y	120, 1251, 1259	121, 122, 123, 1200
Stable angina pectoris or CABG/PCI procedures	DNPR/ICD-10	10y	120, 1251, 1259	121, 122, 123, 1200
	DNPR/Procedure	10y	KFNA, KFNB, KFNC, KFND, KFNE, KFNF, KFNG, KFNH20	I21, I22, I23, I200 (any diagnosis during hospital contact with
				contact the proc

				or within 10
				years before
Myocardial infarction	DNPR/ICD-10	10y	121, 122, 123	
Heart failure	DNPR/ICD-10	10y	150	
Stroke	DNPR/ICD-10	10y	160, 161, 163, 164	
Atrial fibrillation/flutter	DNPR/ICD-10	10y	148	
Heart valve disease	DNPR/ICD-10	10y	105, 106, 107, 108, 109.8, 134-137, 139, 151.1A, Q22, Q23	
Venous thromboembolism	DNPR/ICD-10	10y	126, 1801, 1802, 1803	
Diabetes	DNPR/ICD-10	10y	E10, E11, E12, E13, E14, O24, G63.2, H360, N083	O24.4
	NPD/ATC	10y	A10A, A10B	
Chronic pulmonary disease	DNPR/ICD-10	10y	J40, J41-J44, J45–J47, J60–J67, J68.4, J70.1, J70.3, J84.1, J92.0, J96.1, J98.2, J98.3	
Markers of smoking (diagnoses or medications for tobacco smoking or	DNPR/ICD-10	10y	J41-J44, F17, Z716, Z720	
chronic obstructive pulmonary disease)				
	NPD/ATC	10y	R03, N07BA	
Obesity diagnoses or medications	DNPR/ICD-10	10y	E66	
	NPD/ATC	10y	A08	
Alcoholism-related diagnoses or medication for alcohol deterrent	DNPR/ICD-10	10y	DF10, DE244, DG312, DG621, DG721, DI426, DK292, DK70, DK852, DK860, DQ860, DZ502, DZ714, DZ721	F100
	NPD/ATC	10y	V03AA, N07BB	
Kidney disease diagnosis	DNPR/ICD-10	10y	112, 113, N00–N05, N07, N11, N14, N18–N19, Q61, N08, E102, E112, E142	
End-stage renal disease (kidney transplant or dialysis)	DNPR/Procedure	10y	BJFD2	
	DNPR/Surgery	10y	KKAS	
	DNPR/ICD-10	10y	T861, Z940	
Liver disease	DNPR/ICD-10	10y	B18, B150, B160, B162, B190, I85, K70, K71, K72, K73, K74, K760, K76.6	
Dementia	DNPR/ICD-10	10y	DF00, DF01, DF02, DF03, DG30, DG310B, DG311, DG318, DG319	
	NPD/ATC	10y	N06D	
Cancer (including metastatic cancer)	DNPR/ICD-10	10y	C00-C96, D459, D46, D471, D473, D474, D475, CxxxM	C44
Concurrent antihypertensive medication (see exposures)	NPD/ATC			

Statins	NPD/ATC	90d	C10AA, C10B
Aspirin	NPD/ATC	90d	B01AC06, N02BA01, N02BA51
Opioid use	NPD/ATC	90d	N02A, N07BC02
Immunosuppressant use	NPD/ATC	90d	L04
Glucocorticoids	NPD/ATC	90d	H02AB
Loop diuretics	NPD/ATC	90d	C03C
Antibiotics	NPD/ATC	10d	J01
Antivirals	NPD/ATC	10d	J05
Vitamin K antagonists	NPD/ATC	90d	B01AA
Antidepressants	NPD/ATC	90d	N06A
Antipsychotics	NPD/ATC	90d	N05A
Hypnotics/sedatives	NPD/ATC	90d	N05C
Marital status	CPR		
Rural/urban place of residence	CPR		

Abbreviations: ATC Anatomical Therapeutic Chemical Classification System; CPR Danish Civil Reigistration System; DNPR Danish National Patient Registry; ICD-10 International Classification of Diseases 10th edition; NPD National Prescription Database.

References:

- 10. Sommerstein R, Gräni C. Rapid response: re: preventing a covid-19 pandemic:

ACE inhibitors as a potential risk factor for fatal Covid-19. https://www.bmj.com/content/368/bmj.m810/rr-2. *BMJ.* 2020.

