4.4. Study population

The source population is all Danish citizens (popuation~5.8 million).²² The study population for risk analysis (the test-negative case-control analysis) will be all patients tested for SARS-CoV-2, while the prognosis analysis (cohort analysis) will only include patients tested positive SARS-CoV-2, *i.e.*, patients with COVID-19.

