4.6. Exposure

The study is designed to address acute effects of current use of ACE-I/ARB, and we do not expect any cumulated effect of long-term ACE-I/ARB use. The half-life of ACE-I/ARB ranges from 1 to 24 hours.

The exposure will be defined by filled prescriptions for ACE-I/ARB and other antihypertensive drugs within 90 days before test for SARS-CoV-2. Data on prescriptions are obtained from the Danish Prescription Registry, which include complete and valid information on all filled prescriptions at community pharmacies in Denmark since 1995.²⁶ Data include, among others, date of dispensing, Anatomical Therapeutic Chemical (ATC) code, and drug quantity.

The main exposures will be:

- Current use (prescription filled within prior 90 days before test) of ACE-I/ARBs, compared with
 - Current use (prescription within 90 days) of calcium channel blockers (CCB), a cardiovascular drug used for similar medical indications as ACE-I and ARB, to assess if any observed association with outcomes is specific to ACE-I/ARB exposure.

• No use of ACE-I or ARB (prescription >365 days or never)

Secondary exposures will be:

- Former versus no use of ACE-I or ARB (former use defined as prescription 91-365 days before test)
- Current ACE-I/ARB use compared with:
 - Current use of thiazides (prescription within 90 days)
 - Current use of beta-blockers (prescription within 90 days)

As an additional analysis, ACE-I and ARB will be analyzed separately if the number of exposed are sufficient.

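### The stated 92% power for a mortality risk ratio of 1.2 does not follow from the protocol's own inputs, which give about 23–27%

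*Protocol*

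**What the plan says.** Protocol section 4.10 reports that on 20 April 2020 "there are 96,224 individuals tested for SARS-CoV-2 and 7,515 are tested positive", with 364 deaths among the positives. It continues: "The proportion of patients using ACE-I/ARB is expected to be 17% and the proportion using CCB is expected to be 7"%, taken from a historical cohort. Then, "Assuming a 30-day mortality of 4% in unexposed", it concludes that "we will have a power of 92% for detecting a RR of 1.2 with an alpha-level of 5"% for current users against non-users, citing EpiSheet.

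Section 4.4 fixes the population for this comparison: the prognosis cohort "will only include patients tested positive SARS-CoV-2". Death within 30 days is the primary outcome (section 4.7).

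Section 4.6 names two main comparators for current ACE-I/ARB use. One is no use; the other is "Current use (prescription within 90 days) of calcium channel blockers (CCB"). Section 4.10 gives power only for the first.

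**The concern.** About 17% of 7,515 patients are exposed and about 4% are expected to die, so the exposed group should have some 60 deaths. A 20% relative increase means about 10 more deaths than under no effect (1,278 × 0.008 = 10.2). A count of around 60 has a Poisson standard deviation of nearly 8, so 92% power is not credible at first sight.

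The study addresses a public drug-safety question, and its results are to go to journals and the Danish Medicines Agency website (section 6). The protocol sets no rule for reading a null result. A power claim of 92% at a risk ratio of 1.2 nonetheless invites readers to treat a null finding as strong evidence against a 20% rise in mortality. Section 4.10 is also where the ENCePP checklist (item 10.2) sends anyone asking about study size.

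**Working it through.** **Inputs** (section 4.10 unless noted)

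- N = 7,515 test-positive patients (population per section 4.4)
- Exposed share 17%: n1 = 0.17 × 7,515 = 1,278; n0 = 0.83 × 7,515 = 6,237
- p0 = 0.04; risk ratio 1.2, so p1 = 0.048 and the difference is 0.008
- Expected deaths: 1,278 × 0.048 = 61 exposed; 6,237 × 0.04 = 249 unexposed
- Alpha 5%, taken as two-sided (z = 1.96) because the planned intervals are 95%

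**Attempt to reproduce 92%**

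1. *Unpooled test.* SE = √(0.048 × 0.952/1,278 + 0.04 × 0.96/6,237) = 0.00647. Power = Φ(0.008/0.00647 − 1.96) = Φ(−0.724) = 23.4%.
2. *Pooled test.* Overall risk = 0.04 × (0.83 + 0.17 × 1.2) = 0.04136. SE under the null = √(0.04136 × 0.95864 × (1/1,278 + 1/6,237)) = 0.00611. Power = Φ((0.008 − 1.96 × 0.00611)/0.00647) = 26.9%.
3. *Log risk ratio.* SE = √(0.952/(1,278 × 0.048) + 0.96/(6,237 × 0.04)) = 0.139. Power = Φ(ln 1.2/0.139 − 1.96) = 25.8%.
4. *Simulation* of the pooled test, 200,000 replicates: 26.6%.

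None is near 92%.

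**Other readings, risk ratio 1.2**

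| Change from the base case | Power |
|---|---|
| One-sided 5% | 34–38% |
| Baseline 4.84% (364/7,515) | 28–31% |
| Equal split of 7,515 | 39% |
| 10,000 positives | 30–34% |
| 15,000 positives | 42–46% |
| All 96,224 tested (wrong population) | over 99% |
| Baseline 10% | 53–58% |

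Holding N at 7,515 and the ratio at 1.2, 92% power would need mortality of about 21–23% in the unexposed, against the 4% stated.

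**What the inputs do support** (unpooled / pooled / log risk ratio)

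| Quantity | Result |
|---|---|
| Risk ratio at 92% power, vs non-use | 1.62 / 1.56 / 1.53 |
| Risk ratio at 80% power, vs non-use | 1.50 / 1.45 / 1.44 |
| Positives needed for 92% at 1.2 | 55,744 / 52,192 / 49,592 |

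**CCB comparison.** CCB users: 0.07 × 7,515 = 526. With the same p0 and p1, power at 1.2 is 11.6% / 10.3% / 11.1%. The ratio detectable at 80% power is 1.78 / 1.86 / 1.93.

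**Interval width.** At a risk ratio of 1.2, SE(log RR) is 0.139 vs non-use and 0.247 vs CCB. The 95% interval is the estimate multiplied and divided by exp(1.96 × 0.139) = 1.31 and exp(1.96 × 0.247) = 1.62. At a risk ratio of 1.0 the factors are 1.34 and 1.64.

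**The case against.** The best defence concerns consequence, not arithmetic. This is a registry study that takes every tested inhabitant in a calendar window, so the power figure sets no recruitment target, stopping rule or analysis. Section 4.9 plans 95% confidence intervals for the outcome risks, so the realised precision should be visible. The protocol speaks of detecting a risk ratio of 1.2, not of excluding one, and how readers would take a null result is an inference. All of this stands, and it limits the harm. It does not make a false statement about the primary outcome acceptable.

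A second defence is that section 4.10 claims nothing about the CCB comparison, so its absence is an omission and not an arithmetic error. That is fair, and the finding does not depend on it. But section 4.6 makes CCB use a main comparator and section 4.10 gives its share, so the figure belongs in the same correction.

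Third, sidedness is not stated, so 23–27% rests on the two-sided reading. True, but one-sided alpha reaches only 34–38%.

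Finally, the cause of the error is unknown. Because 92% fits a ratio of about 1.53–1.62, a mistyped ratio or input is possible, and the sponsor should look at the EpiSheet entries before replacing the number.

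**Conclusion.** The 92% is wrong as written. The protocol's own inputs give about 23–27% two-sided power, a gap of at least 65 percentage points in the favourable direction, in the only power statement for the primary outcome. On those inputs the study has good power only for increases of roughly 45–50% versus non-use, or 80–90% versus CCB users.

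This rests on the section 4.10 inputs taken at face value, two-sided alpha of 5% and a crude two-group comparison. At the stated 4% mortality it is probably optimistic. Section 4.6 keeps former users (91–365 days) out of the non-user group, so 6,237 is an upper bound, and the weighting in section 4.8.1.1 will usually lower the effective sample size. The CCB figures count all 526 users; the protocol gives no share who also take ACE-I/ARB, and removing them would lower power further.

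**What to change.** Check the EpiSheet entries, then replace the power sentence in section 4.10. On the present inputs the text should state:

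- two-sided alpha of 5%, and power of about 25% for a risk ratio of 1.2 versus non-use;
- risk ratios detectable at 80% power: about 1.45–1.5 versus non-use and about 1.8–1.9 versus CCB use;
- expected 95% interval factors at a risk ratio of 1.2: about 1.31 versus non-use and 1.62 versus CCB use, before any loss from weighting;
- that a non-significant result will be interpreted through its confidence interval, and not as evidence that the risk ratio is below 1.2.

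The first item is the essential correction; the others tell readers what the study can show. If the number of positives is larger when the data are cut, recalculate with that number.

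The cost is protocol wording, recorded in section 7. No patients, data or analyses are added. The stated power becomes much less favourable.

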4.9. Statistical analyses

In the analyses of prognosis, patients will be followed from day of SARS-CoV-2 positive test result and until date of hospital admission, ICU admission (in analysis of ICU admission), date of death, end of follow-up or for up to 30 days.

Patient characteristics will be tabulated according to each exposure group.

Descriptive analyses will explore the timing of outcomes one month prior to and three months after the first positive test for SARS-CoV-2. In case of a substantial fraction of outcomes having occurred in the days leading up to a positive test, a post-hoc analysis with a larger follow up windows (pre- and post-test) will be conducted.

For each exposure group, we will estimate the 30-day PS-weighted cumulative incidence (risk) of of death, and of each of the non-fatal events (hospital admission, ICU admission, ICU+MV, ICU+inotropes/vasopressors, RRT) accounting for competing risk by death. All 95% confidence intervals will be computed using bootstrapping. The risk of each outcome within 30 days will be computed with 95% CI.

Propensity scores for each comparison (e.g. current ACE-I/ARB use vs. current CCB use) will be computed using logistic regression including all the potential confounders as described above. All other exposures (anti-hypertensive drugs) will be included in the PS-model. The propensity score weighted (SMRW=ATT) cumulative incidence (risk) of each outcome will be plotted and estimated with 95% CI estimated by bootstrapping. The adjusted (PS weighted) risk difference will be computed for the 0-30 period.

The 30-day risk will be compared using PS weighted log binomial regression to estimate risk ratio for death, hospital admission, ICU admission, ICU+MV, RRT, and ICU+inotropes/vasopressors.

Subgroup analysis will be conducted to address effect modifiers including age group (=<65, >65 years) and in patients with assumed uncomplicated hypertension as the primary indication for treatment, defined as patients without any history of diabetes, renal disease, angina pectoris, myocardial infarction, or heart failure. We will also stratify by ABO blood type, if available, because blood type is suggested to be associated with ACE2.³⁰

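### Section 4.6 names calcium channel blockers as a class, but no row of the code table contains C08D, so single-agent verapamil or diltiazem is neither comparator nor covariate

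*Protocol*

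**What the plan says.** Protocol section 4.6 compares current ACE-I/ARB use with current use of "calcium channel blockers (CCB), a cardiovascular drug used for similar medical indications as ACE-I and ARB". It sets no limit to a subclass. The code table (headed Codes, cited as the Appendix in sections 4.8.1.1 and 4.9) has a row with the same general label, whose inclusion codes are "C07FB, C08CA, C09BB, C09DB, C09DX01" with a 90-day look-back and no exclusions.

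Section 4.9 says of the propensity score: "All other exposures (anti-hypertensive drugs) will be included in the PS-model". The covariate part of the code table adds no further antihypertensive codes. It has one line, "Concurrent antihypertensive medication (see exposures"), which points back to the exposure rows. The count of antihypertensives is built from the same rows: "0-5 (see below: ACE-I/ARB, CCB, Thiazides/diuretics, BB, other antihypertensives"). The row that might have served as a catch-all, other antihypertensives, lists "C02AC, C02CA, C03BA11, C09XA C02AB01".

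**The concern.** The text and the code list do not describe the same comparator. In the ATC system, which the protocol adopts for its drug codes, C08CA holds the single-agent dihydropyridines and C08D holds verapamil and diltiazem. A reader of section 4.6 would expect all of these to count as CCBs, but only C08CA and certain fixed combinations do.

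The omission from the comparator could be a design choice, although the protocol does not say so. The omission from the covariates is harder to explain. The hypertension covariate is limited to hospital diagnoses, so filled prescriptions are one of the few markers of cardiovascular disease treated elsewhere. Section 4.8.1 treats confounding by indication as a central problem. A drug that is in no row cannot be adjusted for, and a balance table limited to the listed covariates cannot show an imbalance in it.

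**Working it through.** No figure in the protocol depends on this row, so there is nothing to reproduce. The check has three parts.

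**1. Which rows capture which codes.** Each ATC code was matched by prefix against every drug row of the code table, exposures and co-medication covariates together.

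| ATC code | Content (ATC system) | Rows matched |
|---|---|---|
| C08CA01 | single-agent dihydropyridine | CCB |
| C08DA01 | verapamil | none |
| C08DB01 | diltiazem | none |
| C09BB10 | ACE inhibitor with verapamil, fixed combination | ACE-I and CCB |
| C07FB02 | beta-blocker with CCB, fixed combination | CCB and beta-blocker |

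The thiazide row, "C03AA01, C03AA03, C03AB01, C03AB03, C03AX01, C03EA, C07B, C09BA, C09DA, C09DX01, C09DX03, C09XA52, C09XA54", has no C08 code. The beta-blocker row is C07 only. The loop diuretic, statin, aspirin and remaining drug covariates have no C08 code either. Verapamil is therefore captured in the ACE-inhibitor combination but not as a single agent.

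**2. What this does in each analysis**, for a patient whose only CCB is a single-agent C08D drug:

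- ACE-I/ARB versus CCB: if not on ACE-I/ARB, the patient is not in the comparator arm. If on ACE-I/ARB, the patient stays in the exposed arm with an antihypertensive count one too low.
- ACE-I/ARB versus no use: the patient stays in whichever group ACE-I/ARB filling dictates, coded CCB = 0.
- ACE-I/ARB versus thiazides or beta-blockers: the patient is coded CCB = 0 in the propensity score.
- Test-negative models: in the comparison with non-use the covariate is again CCB = 0, and in the comparison with CCB the patient is not counted as a CCB user.

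A patient who also fills a C08CA drug or a listed combination is still coded as a CCB user and is unaffected.

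**3. Size.** Section 4.10 gives 7,515 test-positive patients and states that "the proportion using CCB is expected to be 7" per cent.

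- Expected CCB users: 0.07 × 7,515 = 526.
- Assume that this 7% counts only users captured by the row, and that C08D users make up a share s of all CCB users. The number missed is then 526 × s/(1 − s).
- s = 2%: 11 patients. s = 5%: 28. s = 10%: 58. s = 20%: 132.

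The documents supply no value of s, so the range 11 to 132 is only illustrative.

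For the effect on the mortality risk ratio, let C08D use have prevalence p₁ in one group and p₀ in the other after weighting, and let it mark a risk ratio of R for death given the other covariates. The bias factor is [1 + p₁(R − 1)]/[1 + p₀(R − 1)]. Both the imbalance and R are assumptions:

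- R = 1.5, p₁ = 3%, p₀ = 2%: 1.015/1.010 = 1.005.
- R = 1.5, p₁ = 2%, p₀ = 0: 1.010/1.000 = 1.010.

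The shift is 0.5% to 1.0% of the risk ratio. Swapping p₁ and p₀ gives the same size in the other direction.

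**The case against.** The strongest reply is that the code table is coherent on its own terms. Section 4.9 puts all other exposures into the propensity score, and the covariate row ties antihypertensive co-medication to the exposure rows. Every class defined there does enter. A reader might infer that section 4.9 promises to adjust for every antihypertensive drug and is contradicted by the code list. The wording does not go that far, and this part of the reply stands.

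A reader might also infer that C08D users are wrongly placed in the no-use group as untreated patients. They are not: section 4.6 defines that group by the absence of ACE-I/ARB filling, so they belong there, and only a covariate value is affected. Nor do the documents support a bias in one particular direction, because C08D goes uncoded in exposed and unexposed patients alike.

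It can further be said that a narrower comparator is defensible, since section 4.8.1 relies on comparator users having hypertension as the indication. That could justify leaving C08D out of the comparator, but not out of the covariates. Finally, beta-blockers, thiazides, loop diuretics, statins, aspirin and vitamin K antagonists are all taken from prescriptions, and hospital codes for angina, atrial fibrillation and hypertension are adjusted for. These capture part of the same indications and make the effect smaller.

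**Conclusion.** The point holds as a gap in the code list and a mismatch between that list and section 4.6. Single-agent C08D drugs are absent from the CCB indicator, the antihypertensive count, the propensity score and the test-negative models. The importance is low. Under the assumed inputs the mortality risk ratio moves by about 1% or less, the direction is unknown, and the other covariates probably absorb some of it. No conclusion of the study should be expected to turn on it.

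This rests on the ATC meaning of C08CA and C08D, which the protocol adopts but does not spell out, and on assumed figures for C08D use and its association with death. It does not rest on any claim that the study groups are misclassified with respect to ACE-I/ARB.

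**What to change.** Add C08D to the code table as its own prescription covariate with a 90-day look-back. Enter it in every propensity-score model, the balance table and both test-negative models, and say whether it adds to the antihypertensive count (which would then run to 6).

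In section 4.6, state that the CCB comparator is defined by the listed codes: C08CA plus the fixed combinations, including C09BB. Calling it a dihydropyridine comparator would not be accurate, because C09BB also takes in an ACE-inhibitor/verapamil combination.

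If the whole class is intended, add C08D to the CCB row instead. The text, the comparator and the count then agree without a new covariate.

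The cost is one ATC code and one sentence. The prescription data are already linked (section 4.3), so no new data are needed.

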4.2. Study period

The study will include patients tested from 27 February 2020 (the date of first identified COVID-19 case in Denmark) to 28 April 2020 (or up to 30 days before manuscript submission) to allow complete follow-up on all included patients.

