4.8.1.1. Propensity score methods

The PS is the probability of being exposed given the covariate pattern for the patient. The PS will be estimated for each patient hospitalization in each of the examined comparisons using a logistic regression model including calendar time and the covariates listed in the Appendix. As we are interested in the average treatment effect in the treated (ATT), we apply PS-weighting using ATT weights to make the number and covariate distribution in the comparison groups resemble that of the ACE-I/ARB users.

8

Overlap in PS distributions will be checked before weighting. Covariate balance will be assessed by standardized differences (SDs), empirical cumulative distribution functions for continuous variables (age and index), and by PS-weight percentiles.

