4.8.2. Selection bias

The risk of selection bias is reduced by including all tested Danish inhabitants. Still, criteria for testing and hospital admission have changed during the study period, which will be addressed in a sensitivity analysis stratified by calendar time. We do not expect that ACE-I/ARB users would be more likely to be tested, and thereby included, as compared to users of other antihypertensive drugs.

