The risk of COVID-19 (a positive test for SARS-CoV-2) will be analyzed using a testnegative case-control design among all patients tested. All covariates will be tabulated for patients with a positive test and negative test for SARS-CoV-2. The odds ratio for current ACE-I/ARB use vs. non-use and CCB use, respectively, will be estimated using two separate logistic regression models adjusted for all covariates, see Appendix.

In a sensitivity analysis, we will explore the robustness of our findings by repeating the analyses in patients who filled a prescription within 120 days before a positive test.

Finally, we will do a sensitivity analysis stratified by calendar time to address changes in testing and hospitalization strategy.

10

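### A single before/after-lockdown cut is the only calendar-time adjustment in the main models and may leave residual confounding, chiefly in the test-negative odds ratio for ACE-I/ARB use versus non-use

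*Protocol*

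**What the plan says.** The covariate section of the Codes table, which the text calls the Appendix, lists "Calendar time (before / after lockdown" as a two-level variable. It gives no lockdown date, and no other form of calendar time appears in the protocol.

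That variable reaches all main analyses:

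- Section 4.8.1.1 estimates each propensity score by a "logistic regression model including calendar time and the covariates listed in the Appendix".
- Section 4.9 estimates the test-negative odds ratios, against non-use and against CCB use, by "two separate logistic regression models adjusted for all covariates, see Appendix".

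Section 4.2 sets inclusion from "27 February 2020 (the date of first identified COVID-19 case in Denmark) to 28 April 2020", or later, which is at least 62 days. Section 4.8.2 states that "criteria for testing and hospital admission have changed during the study period, which will be addressed in a sensitivity analysis stratified by calendar time". Section 4.9 repeats the commitment: "we will do a sensitivity analysis stratified by calendar time to address changes in testing and hospitalization strategy". Neither place defines the strata.

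Section 4.8.2 adds: "We do not expect that ACE-I/ARB users would be more likely to be tested". That expectation is stated relative to users of other antihypertensive drugs. Nothing is said about non-users, who are a main comparator in sections 4.6 and 4.9.

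**The concern.** In a test-negative design, test date can drive both the chance of a positive result and the mix of people tested, including how many use ACE-I/ARB. If both move with time inside the before or the after period, a two-level term pools days that differ. An association can then appear without any drug effect, in either direction. The plan itself names changing testing criteria, and the test date is necessarily held, because exposure windows (section 4.6) and follow-up (section 4.5) are counted from it.

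At stake is the third aim, where precision is high enough for a modest bias to matter. For ACE-I/ARB use versus everyone else, the 95% confidence interval of the odds ratio is only about ±6.5% wide.

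**Working it through.** **Inputs from section 4.10.** 96,224 tested and 7,515 positive (7.8%), hence 88,709 negative; 17% expected to use ACE-I/ARB and 7% CCB. The protocol gives no figure for time trends or for bias, so there is nothing of its own to reproduce on this point. All trends below are assumptions, and the true odds ratio is 1 throughout.

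**Precision.** SE(log OR) = √[1/(7,515×0.17) + 1/(7,515×0.83) + 1/(88,709×0.17) + 1/(88,709×0.83)] = 0.032. Then exp(±1.96×0.032) gives 0.94 to 1.06. With 17% versus 7% in place of 17% versus 83%, and overlap between the drugs ignored, the SE is 0.054, or roughly ±11%.

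**Check A: daily model.** Over 62 days, tests per day rise linearly. On the logit scale, positivity on day d is a + ln(r_p)·f(d) and exposure is b + ln(r_e)·f(d). The constants a and b are set so that the totals are 7.8% and 17%. The odds of positivity fall to 1/2 or 1/4 and the odds of exposure rise 1.25- to 2-fold. The shape f(d) is either linear or a hump centred on day 30. Lockdown is placed at day 14 or day 21. The exposure odds ratio was fitted to expected counts:

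| Trend | Unadjusted | Before/after term | Week indicators |
|---|---|---|---|
| Positivity or exposure constant | 1.000 | 1.000 | 1.000 |
| Linear | 0.990 to 0.937 | 0.995 to 0.960 | 0.999 to 1.000 |
| Hump-shaped | 0.982 to 0.898 | 0.983 to 0.900 | 0.995 to 0.999 |

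The binary term removes part of a linear trend and almost nothing of a hump. All values lie at or below 1 because positivity and exposure were assumed to move in opposite directions. Trends in the same direction would push the odds ratio above 1.

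**Check B: three phases** of 25,000, 45,000 and 26,000 tests, with the odds ratio equal to 1 within each. In the first scenario below, the exposed positives are 770 + 535.5 + 101.4 = 1,406.9, the unexposed positives 6,023.1, the exposed negatives 15,123.1 and the unexposed negatives 73,446.9. The crude odds ratio is (1,406.9×73,446.9)/(6,023.1×15,123.1) = 1.134.

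Adjustment for one cut uses the Mantel-Haenszel estimate, Σ(ad/T)/Σ(bc/T). With the cut after phase 1, this is (516.5 + 508.4)/(516.5 + 482.1) = 1.026.

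| Positivity % / exposure % by phase | Crude | Cut after phase 1 | Cut after phase 2 |
|---|---|---|---|
| 14, 7, 3 / 22, 17, 13 | 1.134 | 1.026 | 1.057 |
| 14, 7, 3 / 14, 17, 20 | 0.915 | 0.978 | 0.964 |
| 12, 8, 5 / 19, 17, 15.5 | 1.031 | 1.007 | 1.012 |

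The crude column equals the result under the planned model only if essentially all tests fall after lockdown, because the binary term is then constant.

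Both checks leave out the other covariates and concern the odds ratio only. The weighted risks were not simulated.

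**The case against.** The strongest reply is that nothing in the protocol shows drift within the two periods. Section 4.8.2 gives no number, date or direction of changes, and a single change at lockdown would fit its wording. Confounding also needs ACE-I/ARB use to drift conditional on the other covariates. The models adjust for age, sex, hypertension, diabetes, heart and kidney disease, statins and other antihypertensives, through which a changed testing mix would mostly act. If the residual drift in exposure were only 18, 17 and 16% with positivity 14, 7 and 3%, even the crude odds ratio would be 1.03. This stands, and it limits the point to possible residual confounding.

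Three stronger readings are tempting, but the documents do not support them:

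- **That confounding is established, at 9% to 13%.** The crude values 0.915 and 1.134 take no account of the lockdown term. With a cut between phases, the same scenarios leave 2% to 6%.
- **That the primary mortality result is affected in the same way.** The prognosis cohort contains only test-positive patients, so the positivity mechanism does not operate there. Admission practice could still vary with time, but no bias in the weighted risks has been calculated.
- **That both comparators are equally exposed.** Differing time drift between two antihypertensive classes is less plausible, section 4.8.2 expects equal testing between them, and the CCB odds ratio is less precise.

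The planned stratified analysis is a partial answer. Stratum-specific estimates do control calendar time to the width of the strata. However, the strata are undefined and would add no finer control if they repeat the lockdown split. Whatever they are, the main estimates stay as they were.

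**Conclusion.** The point holds in limited form. The protocol fixes a two-level calendar term in all its main models while stating that testing and admission criteria changed during the period. This may leave residual confounding, chiefly in the test-negative odds ratio against non-use.

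The size is zero if exposure among the tested, or positivity, does not drift within the two periods. It is up to about 6% under the smooth and phased trends assumed here, and up to about 10% with a hump-shaped trend. If almost no tests precede lockdown, the binary term does nothing and the crude bias remains. All these figures rest on assumed trends, an assumed lockdown date and no adjustment for other covariates, which would lower them. Direction cannot be determined. The change is worth making because it is cheap, harmless if there is no drift, and removes nearly all of the bias in every scenario tried (0.995 to 1.000 with week terms).

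**What to change.** In the covariate list, replace the two-level term by test date, and take it from the test record. The list names the patient registry (DNPR) as the source of calendar time, whereas section 4.3 takes test data from the microbiology database.

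- **Test-negative logistic models:** calendar weeks or a restricted cubic spline of test date. Nine weeks need eight indicators, negligible against 96,224 tests and 7,515 positives.
- **Propensity score models:** a low-df spline. Week indicators may be sparse in the early weeks, since only about 7,515 × 0.07 = 526 CCB users are expected among the positives.
- **Sensitivity analysis:** define the calendar strata with dates, finer than the lockdown split, and state the lockdown date if that split is still reported.

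The cost is a short edit to the covariate list and section 4.9 and a few extra model parameters. No new data are needed.
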